**I. Analysis Plan**

Power Analysis

Power estimates for this study were based on prior work by Lee et al. In their study, patients were randomly assigned to receive morphine with naloxone or morphine without naloxone. They found that those who received naloxone had a shorter time to first postoperative passage of flatus ( $M = 51.9$ hr,  $SD = 16.6$ hr) versus control ( $M = 87.0$ hr,  $SD = 19.5$ hr). Similarly, the authors found that time to first feces was faster in the naloxone cohort ( $M = 95.3$ hr,  $SD = 25.0$ hr) than control group ( $M = 132.9$ hr,  $SD = 29.4$ hr). However, their study duration was exceedingly long with a maximum duration of approximately 160-180 hours. One goal of this study is to estimate the effect of naloxone on time to first feces within the first 120 hours (5 days) following treatment. In this study, patients who require a second intervention or who do not experience flatus or feces by Day 5 will be censored.

The null hypothesis is that the bowel movement (BM) rate is identical in the two groups (control and naloxone). Power is computed to reject this null hypothesis. Computation of power is based on a hazard ratio of 1.508. Specifically, it assumes instantaneous BM rates of 0.160 for the control group versus 0.241 for the naloxone group. This is equivalent to a median time of no BM of 4.34 days for the control group versus 2.879 days for the naloxone group. At 5 days, it is hypothesized that 45% of the control cohort versus 30% of the naloxone cohort will require a second intervention because they have not experienced a BM.

With a total of 150 patients entered into the naloxone group and a total of 150 historical controls, the study will have power of 80.1% to yield a statistically significant result. The

criterion for significance (alpha) is set at 0.050, and the test will be 2-tailed meaning an effect in either direction will be interpreted.

#### Analysis Plan

Two different approaches will be used for the primary aim. First, a paired *t*-test will be used to estimate the mean difference in hours to first feces between the active cohort and historical control cohort. For this analysis, the origin of time for both groups is start of surgery. If necessary, a Wilcoxon signed ranks test will be used to compare the two distributions.

A second approach will compare the instantaneous rates of bowel movements between the active and control cohorts using a Frailty survival model that allows for clustering of patients within their matched strata. In this analysis, control patients who required treatment for ileus will be censored at the time of such treatment, and active patients who require an additional treatment beyond receipt of naloxone will be censored at the time of such treatment. All patients who do not achieve BM by 120 hours will also be censored. Hours to first feces for both groups will be start of surgery. While we assume there is no immortal time bias between start of surgery and receipt of naloxone for the active cohort, a conditional landmark method may be used to account for the amount of hours between surgery and receipt of naloxone. The proportional hazards assumption for all predictors will be tested using Martingale residuals as described by Lin, Wei, and Ying.

Regarding the secondary aims, a linear mixed effects model will be used to compare LOS between the two groups. A generalized linear mixed effects model will be used to compare the two groups on all other secondary outcomes. In these models, random intercepts will be allowed for each case-control matched strata in order to account for the correlation between cases and controls based on age, gender, Charleston co-morbidity index, and operation time under anesthesia.

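### The first-listed analysis of the primary aim, a paired t-test, cannot use censored times; the plan gives no rule for patients without a bowel movement and does not say which of its two analyses decides.

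*Combined protocol and SAP*

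**What the plan says.** The Study Design section names one primary outcome, time to first BM in hours. The Analysis Plan then states: "Two different approaches will be used for the primary aim". The first is a paired t-test, which "will be used to estimate the mean difference in hours to first feces between the active cohort and historical control cohort". It has a fallback: "If necessary, a Wilcoxon signed ranks test will be used to compare the two distributions". The second is a frailty survival model that allows for the matched strata.

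Censoring is described in two places.

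- The Power Analysis, speaking of the study as a whole: "In this study, patients who require a second intervention or who do not experience flatus or feces by Day 5 will be censored". It gives one goal as to "estimate the effect of naloxone on time to first feces within the first 120 hours (5 days) following treatment", and it expects 45% of controls and 30% of naloxone patients to have had no BM at 5 days.
- The Analysis Plan, under the survival model only. The rule for the naloxone group reads: "active patients who require an additional treatment beyond receipt of naloxone will be censored at the time of such treatment". The rule for the historical group names a different trigger: "control patients who required treatment for ileus will be censored at the time of such treatment". Everyone without a BM by 120 hours is also censored.

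The Power Analysis states one null hypothesis, equal BM rates in the two groups, with a hazard ratio of 1.508, 150 patients per group, two-sided alpha 0.050 and power of 80.1%. Nothing in the document ranks the two analyses, says when the signed-rank test takes over, or gives the value that a censored patient contributes to either paired test.

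**The concern.** A paired t-test works on one difference per pair, so both members need a number. By the plan's own forecast most pairs will have at least one member with no BM time by Day 5. The signed-rank test does not help, because it also needs a difference for each pair.

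The analyst must therefore supply a rule. Dropping incomplete pairs selects patients on the outcome itself: the slow patients, whom the drug is meant to help, leave the analysis. Setting non-events to 120 h keeps every pair but estimates a different quantity, the difference in mean time restricted to 120 h. For patients censored earlier, at an additional treatment, it becomes a failure rule that also needs to be stated. If the rule is chosen after the data are seen, the same patients can give a first-listed primary result that is usually null or usually significant. With no ranking, nothing in the text settles what the study concludes when the two analyses disagree.

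**Working it through.** **Inputs from the Power Analysis.** BM rates 0.160/day (control) and 0.241/day (naloxone); hazard ratio 1.508; no BM at 5 days 45% and 30%; 150 per group; two-sided alpha 0.050.

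**Assumptions.** Exponential times, as the plan's constant rates imply; no censoring before 120 h; independent pairs unless stated. The plan gives no within-pair correlation, so 0.3 and 0.5 are also shown.

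**1. The plan's own figures.** No BM at 5 days: exp(−5 × 0.160) = 0.449 and exp(−5 × 0.241) = 0.300. Medians: ln 2/0.160 = 4.33 days and ln 2/0.241 = 2.88 days, which match the text apart from rounding of the rates. Expected events: 150 × 0.55 + 150 × 0.70 = 187.5. Schoenfeld power = Φ(½ × √187.5 × ln HR − 1.96):

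- HR 1.508: Φ(6.847 × 0.4108 − 1.96) = 80.3%
- HR 0.241/0.160 = 1.506: Φ(6.847 × 0.4096 − 1.96) = 80.1%

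The stated 80.1% reproduces and belongs to the hazard comparison. The plan gives no power for the paired t-test.

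**2. Pairs with both times observed.** 0.55 × 0.70 = 0.385, and 0.385 × 150 ≈ 58. The other 92 or so pairs (61.5%) have at least one censored time.

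**3. Rule A: drop incomplete pairs.** Mean among those with a BM by T = 5 days is 1/λ − T·exp(−λT)/(1 − exp(−λT)), which gives 52.1 h and 48.2 h, a difference of 3.9 h. The SD of a pair difference is 47.8 h, so with 57.75 pairs the standard error is 6.3 h and the ratio 0.61. Power by normal approximation is about 9%; simulation gives 9.2%.

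**4. Rule B: set non-events to 120 h.** Restricted mean is (1 − exp(−λT))/λ, which gives 82.6 h and 69.7 h, a difference of 12.9 h. The SD of a pair difference is 60.4 h, standard error 60.4/√150 = 4.93 h, ratio 2.61. Power by normal approximation is 74%; simulation gives 72–73%. The signed-rank test under this rule also has about 73%.

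**5. Rule C: use actual BM times, however late.** Means 24/0.160 = 150.0 h and 24/0.241 = 99.6 h, a difference of 50.4 h. The SD of a pair difference is √(150.0² + 99.6²) = 180.0 h, standard error 14.7 h, ratio 3.43. Power is 93% by normal approximation and 94% in simulation.

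**6. Sensitivity to assumptions (simulated, 4,000 trials per cell).**

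| Within-pair correlation (assumed) | 0 | 0.3 | 0.5 |
|---|---|---|---|
| Complete pairs | 58 | 64 | 69 |
| Rule A: difference | 3.7 h | 5.8 h | 7.3 h |
| Rule A: power | 9% | 18% | 31% |
| Rule B: power | 72% | 84% | 92% |
| Hazard test, pair-robust log-rank as stand-in for the frailty model | 79% | 88% | 95% |

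With Weibull shapes 1.5 to 3 in place of exponential times (same day-5 proportions and hazard ratio, independent pairs), rule A gives 2.7–3.6 h with about 9% power and rule B gives 7.1–10.8 h with 66–71%. The gap between the rules remains.

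**The case against.** **The deciding test is already clear.** The Power Analysis has one null hypothesis, one alpha and one power figure, and all concern BM rates. That is a strong implication, and the powered analysis is sound. But the Analysis Plan puts the other test first and ranks neither, so the implication needs to be written down.

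**The t-test may be meant to use actual BM times.** The detailed censoring rules sit under the survival model, so the first analysis can be read literally as hours to first BM with no cut-off (rule C). For this reason it would go too far to say that the test must fail, or that dropping pairs and setting 120 h are the only options. Against this reading, the Power Analysis applies censoring to the study as a whole, and no follow-up for BMs after 120 h is described. The reading adds a third candidate answer rather than settling the matter.

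**The obvious 120 h rule works well enough.** Largely true: under it the t-test is only modestly less powerful than the hazard test. With equal random censoring of 25% or 50% (assumed) of patients still without a BM at 72 h in both groups, the difference barely moves, to 12.7 or 12.6 h. But the plan does not state this rule.

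**Two stronger inferences do not hold.** A reader might infer that two primary tests inflate the type I error. No passage allows success on either test, so the documents do not support that claim. A reader might also infer that the different censoring triggers in the two groups would create a false benefit in the t-test. That needs a censoring time to be analysed as if it were a BM time, which no passage proposes, together with early censoring assumed in the naloxone group alone.

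**Conclusion.** The point stands as a mismatch between the first-listed analysis and the plan's own censored outcome, together with a missing ranking. Depending on an unstated rule, the paired t-test estimates about 3.9 h (9% power), 12.9 h (about 73%) or, on a reading that conflicts with the Power Analysis, 50.4 h (about 93%). These figures rest on the plan's rates, exponential times, independent pairs and no censoring before 120 h. Within-pair correlation raises the power under every rule but does not bring the rules together.

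A reader might infer that the study is wrongly sized. It is not: the 80.1% reproduces, and 150 per group remains right for the hazard comparison under the plan's inputs.

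**What to change.** 1. Name the matched frailty survival model as the single primary test at two-sided 0.05, in line with the stated null hypothesis and power.
2. Remove the paired t-test and signed-rank test from the primary aim. In their place report, as a supporting estimate with no significance claim of its own, the Kaplan-Meier difference in restricted mean time to first BM up to 120 h, with a confidence interval from a bootstrap that resamples matched pairs. This keeps a result in hours, uses every patient, and fits the plan's 120-hour goal.
3. Where BM times after an additional treatment are recorded, add a sensitivity analysis of both estimates that does not censor at that treatment and counts the first BM up to 120 h. Treatment given because no BM has occurred may make the censoring informative.

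A smaller repair would be to keep the t-test as supportive with non-events set to 120 h. That closes the gap in wording, but the Kaplan-Meier estimate handles earlier censoring without assigning a time to those patients.

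Cost: plan wording and a few lines of code, with no change to the sample size. Items 1 and 2 use the primary outcome and the censoring times that the survival model already needs. Item 3 depends on whether later BM times exist, including in the historical charts and after discharge, which the plan does not promise. One familiar test is lost, and the estimate in hours refers to the first 120 h only.

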### Screening procedures

Patients will be screened at the pre-operative clinic visit based on the inclusion and exclusion criteria.

Historical controls will be identified by a report of patients undergoing spinal fusion procedures

identified via ICD9 codes in the previous 3 years. ICD-9 codes include a short fusion surgery (81.06, 81.62) with 3 or fewer vertebral body segments, long fusion surgery (81.63, 81.64), more than 4 vertebral segments, anterior approaches (81.06) and posterior approaches (81.07) in the thoracic and lumbar spine. The historical controls will be matched to active participants based on age, gender, Charleston co-morbidity index, complexity of surgery, and duration of surgery.

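### The matching factors enter the models only through a stratum term, so a systematic difference left after matching would stay in the naloxone effect

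*Combined protocol and SAP*

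**What the plan says.** Screening procedures states that historical controls will be "matched to active participants based on age, gender, Charleston co-morbidity index, complexity of surgery, and duration of surgery". It gives no caliper, no rule on which factors must match exactly, no algorithm and no size for the control pool.

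The Analysis Plan has two approaches to the primary aim. The first is a paired t-test, with a signed-rank test if needed. The second compares bowel movement rates "using a Frailty survival model that allows for clustering of patients within their matched strata". Secondary outcomes go to mixed models with a random intercept per matched stratum, whose stated purpose is to account for correlation between cases and controls arising from "age, gender, Charleston co-morbidity index, and operation time under anesthesia".

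That second list has four factors, not five. Complexity of surgery is missing, and anesthesia time stands where Screening procedures has duration of surgery. No model names any matching factor as a fixed effect. The proportional hazards check is said to cover all predictors, but none is listed.

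**The concern.** The trial is not randomised (Study Design), so matching and modelling have to make the two cohorts comparable. Matching on five factors at once, at least two of them continuous, with no stated tolerance can leave pairs that are only roughly alike. If the leftover differences lean one way, the model has to deal with them, and a stratum term cannot. Each pair holds one naloxone patient and one control, so whatever the pair shares is the same on both sides of the comparison.

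The documents give some reason to take this seriously. Naloxone patients are approached at a clinic visit 1 to 12 weeks before surgery and must consent (Study recruitment). Controls come from a procedure-code report over the previous 3 years, with no such filter stated. The Background section itself cites duration of surgery as raising the incidence of ileus. What is at stake is whether the reported hazard ratio measures naloxone alone, or naloxone plus a remaining difference in case mix.

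**Working it through.** **1. The plan's own figure.** Inputs from Power Analysis:
- "With a total of 150 patients entered into the naloxone group and a total of 150 historical controls"
- "Computation of power is based on a hazard ratio of 1.508"
- "it assumes instantaneous BM rates of 0.160 for the control group versus 0.241 for the naloxone group"
- 45% and 30% without a bowel movement at 5 days
- "criterion for significance (alpha) is set at 0.050, and the test will be 2-tailed"

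Expected events = 150 × (0.55 + 0.70) = 187.5. The Schoenfeld formula gives power = Φ(ln 1.508 × √187.5 / 2 − 1.96) = Φ(0.411 × 6.85 − 1.96) = 80.3%. The plan says "the study will have power of 80.1% to yield a statistically significant result", so its figure reproduces and is not in dispute.

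**2. How leftover imbalance enters.** Suppose a factor changes the log hazard of bowel movement by β per SD, and naloxone patients differ from their controls by d SD on average. The group log hazard ratio then shifts by about β × d, summed over factors. A shared frailty leaves this shift in place.

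**3. Size under assumed inputs (not in the documents).** Take three factors with a log hazard effect of 0.2 per SD each, all signed to favour naloxone. Starting differences between cohorts of 0.2 to 0.4 SD, with optimal 1:1 matching of 150 patients from pools of 300 to 900, left 0.03 to 0.15 SD of imbalance in simulation.
- Low end: 3 × 0.2 × 0.03 = 0.018, HR = exp(0.018) = 1.02.
- High end: 3 × 0.2 × 0.15 = 0.09, HR = exp(0.09) = 1.09.
- Simulated with a Cox model and a true HR of 1.0: mean HR 1.02 to 1.10 without covariates (largest log HR 0.094), and 0.99 to 1.02 with the five factors added.

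**4. Type I error.** With both groups at 0.160 per day, null events = 300 × (1 − exp(−5 × 0.160)) = 165, so SE = 2/√165 = 0.156.
- Shift 0.018: 0.018/0.156 = 0.12 SE, two-sided error about 5%.
- Shift 0.094: 0.094/0.156 = 0.60 SE. Error = 1 − Φ(1.96 − 0.60) + Φ(−1.96 − 0.60), about 9%.

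**5. Does this hold for a frailty model, and not only a Cox model?** A shared gamma frailty model was simulated with 150 pairs, 5-day censoring and 400 runs. One factor had HR 0.7 per SD and a 0.25 SD within-pair difference. Expected shift: 0.357 × 0.25 = 0.089, HR 1.09.

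| True HR | Mean HR, stratum term only | Mean HR, stratum term plus covariate |
|---|---|---|
| 1.0 | 1.09 | 1.00 |
| 1.508 | 1.66 | 1.52 |

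False-positive rates under the null were 7.2% and 6.0%, against 8.8% by direct calculation for the unadjusted model. Simulation error at 400 runs is about 1.1 points (√(0.05 × 0.95/400)). The bias in the hazard ratio is clear; the false-positive rates are only approximate.

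**6. The opposite direction.** If the same shift of 0.089 ran against naloxone, power would be Φ((0.411 − 0.089) × √187.6 / 2 − 1.96), about 60% instead of 80.3%.

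**The case against.** The strongest reply is that poor matching is nowhere documented. Closeness is unstated, not shown to be bad. Gender is binary, surgery type is described through procedure codes, and one control per patient makes close matching easier than several would. Random leftover differences add noise, not bias. The Background section links duration of surgery to ileus, not to time to first bowel movement. All of this stands, which is why the point is conditional.

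Three stronger readings are tempting and are not supported:
- **That exact matching is impossible, or that the estimate will be biased.** The documents show neither a systematic residual difference nor its direction.
- **That type I error reaches 11%, or 20%.** The first is a simulated worst case from 150 runs, with a 95% interval of about 6% to 16%; direct calculation gives about 9%. A separate run of a comparable design gave HR 1.09 and 8.2% error only for the smallest pool with the largest shift (400 runs). Elsewhere it gave HR 1.02 to 1.05 and no clear inflation. The 20% needs a 0.5 SD within-pair difference, more than three times the 0.15 SD maximum left by matching. Likewise, the worst-case shift is 23% of the planned effect (0.094/0.411), but that is one corner of assumed inputs.
- **That the plan rules out covariates.** The mention of predictors in the plural suggests that more terms may be intended. But a set that is not listed is not pre-specified, and the choice stays open until the data are seen.

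A last objection also stands: five covariates in every secondary model would be too many. Ileus and adverse effects may be sparse, and two secondary outcomes have no counterpart in controls.

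**Conclusion.** The point holds in conditional form. As written, both primary approaches and the mixed models rely on matching of unstated closeness, and none is specified to adjust for what matching leaves behind. If residual differences are systematic and prognostic, the naloxone effect is biased. The 1.02 to 1.10 range for a true null rests on the assumed effects, cohort differences and pool sizes set out above. It illustrates scale and does not predict this trial's bias. That a stratum term alone does not remove such a difference, while a covariate does, follows from the model structure and was confirmed by simulation. The mismatch between the two factor lists needs no assumption and should be reconciled in any case, though by itself it does not show bias. The change is worth making because it uses data the matching already requires.

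**What to change.** In the Analysis Plan:
- **Frailty model.** Keep the stratum term. Add age, gender, comorbidity index, complexity of surgery and duration of surgery as fixed effects, defined as for matching. Make the adjusted hazard ratio the reported result of this approach, and list these terms as the predictors in the proportional hazards check.
- **Secondary models.** Do the same for length of stay and for outcomes with enough events. Use a reduced set or no covariates for sparse binary outcomes. Leave number of naloxone doses and study drug discontinuation out of the between-group models.
- **Paired t-test (or signed-rank test).** Label it as unadjusted.
- **Matching.** State the tolerance for each factor, use one factor list throughout, and report standardised differences after matching.

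The cost is wording, a little more analysis and a few degrees of freedom. With about five added parameters plus group, 187.5 planned events leave about 31 per parameter (187.5/6). No new data are needed.

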### **I. Study Design**

This is a prospective, historically controlled observational trial of enteral naloxone use in patients admitted for spinal fusion surgery and receiving opioids for pain management.

Primary outcome: Time to first bowel movement (hours)

Secondary outcomes:

- Hospital length of stay
- Incidence of post-operative ileus. Post-operative ileus will be diagnosed through a combination of clinical exam and radiographic (X-ray) findings
- incidence of post-operative constipation (defined as 3 days without a bowel movement)
- average numerical pain scale (Adult Nonverbal Pain scale or Visual Analog Scale) on post-operative days 0, 1, 2, and 3
- average daily opioid requirement on post-operative days 0, 1, 2 and 3 (morphine equivalents)
- number of naloxone doses administered
- average number of daily bowel movements,
- number of medication escalations required (defined as use of an as needed laxative medication or addition of a new order for a laxative medication)
- Incidence of adverse effects
- Incidence of study drug discontinuation

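### The frailty model, as written, censors controls at treatment for ileus but naloxone patients at any additional treatment, so the hazard ratio can move from 1 without a drug effect

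*Combined protocol and SAP*

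**What the plan says.** The Analysis Plan names two approaches to the primary aim: a paired t-test, and a "Frailty survival model that allows for clustering of patients within their matched strata". For the second it sets the censoring rule by cohort. For controls, "control patients who required treatment for ileus will be censored at the time of such treatment". For the naloxone cohort, "active patients who require an additional treatment beyond receipt of naloxone will be censored at the time of such treatment". A third rule applies to both: "All patients who do not achieve BM by 120 hours will also be censored".

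The Power Analysis states a single rule without distinguishing cohorts: "patients who require a second intervention or who do not experience flatus or feces by Day 5 will be censored". Its only figures on such treatment are these: "At 5 days, it is hypothesized that 45% of the control cohort versus 30% of the naloxone cohort will require a second intervention". The sample size rests on this type of model: "Computation of power is based on a hazard ratio of 1.508".

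No section defines treatment for ileus, additional treatment or second intervention for the purpose of censoring. Study Design keeps two related outcomes apart. One is ileus: "Post-operative ileus will be diagnosed through a combination of clinical exam and radiographic (X-ray) findings". The other is medication escalation, meaning use of an as-needed laxative or a new laxative order. Study Assessments and Activities has the usual bowel medications ordered for all patients from standard order sets.

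**The concern.** Treatment for ileus is a narrower event than any treatment beyond naloxone. Under the literal text, a laxative given to a patient without ileus ends follow-up in the naloxone cohort and not in the control cohort. Two distortions can follow, with a hazard ratio above 1 favouring naloxone:

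- If the additional treatment speeds the first bowel movement (BM), the accelerated BMs count for controls but not for naloxone patients. The hazard ratio falls.
- If it goes mainly to patients with slow bowels, those patients leave the naloxone risk set and remain in the control risk set. The hazard ratio rises.

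Both can act at once and partly cancel. There is no distortion if the treatment neither changes the BM rate nor depends on bowel speed, or if it is given only at the day-5 cutoff, when everyone is censored anyway. The documents do not say which case applies. Because the study is unblinded and the trigger undefined, its meaning could also be settled during chart abstraction, after outcomes are visible.

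**Working it through.** **1. The plan's own power.** Inputs from the Power Analysis: rates 0.160 and 0.241 per day, 150 per cohort, 5 days, hazard ratio 1.508, two-sided alpha 0.05.

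- Without BM at day 5: exp(−0.160 × 5) = 44.9% and exp(−0.241 × 5) = 30.0%, matching the stated 45% and 30%.
- Events: 150 × 0.551 + 150 × 0.700 = 187.6 (from unrounded proportions).
- Schoenfeld: Φ(√187.6 / 2 × ln 1.508 − 1.96) = Φ(0.85) = 80.3%, against 80.1% stated.

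The stated power is therefore reproduced with no censoring before day 5.

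**2. Null simulation of the rule as written.** All treatment inputs are assumptions. There were 150 matched pairs, exponential BM times, follow-up to day 5, and gamma shared frailty by pair with a likelihood-ratio test; 2,000 trials per cell. A check on data with true hazard ratio 1.5 and frailty variance 1 returned 1.52 and 0.99.

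- Scenario A: one patient type, BM 0.16/day, ileus treatment 0.02/day, escalation 0.2/day.
- Scenario B: half slow (BM 0.08/day) and half fast (0.30/day); ileus treatment 0.04 and 0.01/day; escalation 0.5 and 0.1/day. Pairs either share the type (B matched) or do not (B unmatched).
- After escalation the BM rate is multiplied by 1, 2 or 3.

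Each cell shows the hazard ratio (two-sided rejection) for multipliers 1 / 2 / 3:

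| Start | A | B matched | B unmatched |
|---|---|---|---|
| Day 1 | 1.00 (5.8%) / 0.87 (13.9%) / 0.79 (31.8%) | 1.11 (10.0%) / 0.97 (5.9%) / 0.89 (9.8%) | 1.12 (9.8%) / 0.99 (5.3%) / 0.90 (9.2%) |
| Day 2 | 1.00 (5.8%) / 0.92 (8.3%) / 0.87 (14.8%) | 1.05 (6.3%) / 0.98 (5.1%) / 0.92 (7.8%) | 1.07 (6.8%) / 0.98 (5.8%) / 0.93 (6.8%) |
| Day 3 | 1.00 (4.8%) / 0.96 (5.9%) / 0.92 (8.2%) | 1.02 (4.8%) / 0.98 (5.7%) / 0.96 (6.1%) | 1.03 (5.6%) / 0.99 (5.3%) / 0.96 (6.9%) |

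Censored before day 5, naloxone against control: 39–45% against 4–7% (day 1), 29–37% against 3–5% (day 2), 19–27% against 2–3% (day 3). A day-4 start, in unadjusted Cox, gave 0.97 to 1.01 with rejection of 4.6% to 5.7%.

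**3. One common rule under the null.** With ileus only, any escalation, or no rescue censoring in both cohorts, the hazard ratio was 0.99 to 1.00 and rejection 4.1% to 5.5% (day-1 and day-3 starts).

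**4. A second set of assumptions.** Unadjusted Cox, base escalation 0.5/day, 15% of control treatments counted as ileus treatment. Across the two mechanisms, the unequal rule gave 0.71 to 1.28 (day 1), 0.80 to 1.15 (day 2), 0.89 to 1.07 (day 3), 0.96 to 1.02 (day 4) and about 1.00 near day 5. With both mechanisms together and a doubled rate, the day-1 figure was 1.08, which shows the partial cancelling.

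**5. Under the planned effect.** Scenario A, multiplier 2, true hazard ratio 1.508, 1,600 trials per cell:

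| Rule | Hazard ratio, day 1 / 2 / 3 start | Power, day 1 / 2 / 3 start |
|---|---|---|
| As written | 1.33 / 1.41 / 1.46 | 44.1 / 60.6 / 71.6% |
| Ileus only, both cohorts | 1.52 / 1.52 / 1.51 | 84.1 / 82.0 / 81.0% |
| No rescue censoring | 1.52 / 1.52 / 1.51 | 84.0 / 82.4 / 81.1% |
| Any escalation, both cohorts | 1.53 / 1.52 / 1.51 | 71.2 / 76.4 / 77.4% |

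**6. Analytic power for a common rule.** With BM rate λ and censoring at rate g from day s, P(event) = 1 − e^(−λs) + e^(−λs) × λ/(λ+g) × [1 − e^(−(λ+g)(5−s))]. For g = 0.02/day and s = 1, 2, 3: 183, 185, 187 events and 79.4, 79.8, 80.1% power. For g = 0.2/day: 151, 168, 179 events and 71.4, 75.8, 78.4%.

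The ileus-only powers in steps 5 and 6 differ because the simulation includes BMs accelerated by the laxative, which add events, and the formula does not.

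**The case against.** The strongest reply is that one rule was meant. The Power Analysis has a single trigger, and the Analysis Plan may only be restating it in words suited to each cohort: beyond usual care for controls, beyond naloxone for active patients. No section links the escalation outcome to censoring. This reading is available, and on it the fault is one of drafting. But the text does not say so, and the protocol elsewhere treats ileus and laxative escalation as different things.

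Second, the 45% and 30% place the second intervention at day 5, where the unequal rule does nothing. That is also possible. Yet both sections list treatment separately from reaching the 120-hour limit, and a separate trigger matters only if treatment can come earlier.

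Third, the large figures come from a corner of the assumptions: the 32% needs a day-1 start and a tripled BM rate. With time zero at start of surgery and naloxone starting the next morning, a day-1 start puts additional treatment at about the first dose. At day 3, the protocol's own constipation threshold, the null distortion is small. This stands, and the sizes should be read accordingly.

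Fourth, a common rule removes the bias only if practice is the same in both cohorts, which historical controls do not guarantee. This stands too. In scenario A with a doubled BM rate, a day-1 start, and escalation of 0.4/day in controls against 0.2/day (null, unadjusted Cox), ileus-only censoring gave 0.91 with 11% rejection. The unequal rule gave 0.80 with 29%. The common rule is better, though not a full cure.

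**Conclusion.** The point holds: the censoring rule is wrong as written and should be fixed. Confidence is high on the mismatch in wording and on its conditional consequence; the size is not known. It depends on when additional treatment starts, how often it is given, whether it speeds BM and who receives it, and the documents give none of these before day 5. Under the assumptions shown, the effect ranges from material at a day-1 start to negligible at day 4, in either direction. If the planned effect is real, the day-3 start that is nearly harmless under the null still lowers power to about 72%, assuming escalation of 0.2/day and a doubled BM rate.

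The scope is limited to the survival model. It is the second of two approaches to the primary aim, but the one that the power calculation is built on. The paired t-test states no rescue-censoring rule and is not affected as written. The stated 80.1% is correct on its own inputs.

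**What to change.** Reconcile the Power Analysis and the Analysis Plan into one censoring rule, defined once and abstracted the same way from both cohorts' records.

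- **Suggested primary rule:** censor both cohorts only at treatment for ileus. Use the ileus definition in Study Design, and state what counts as treatment for it and which time is recorded. This keeps the control rule and narrows the naloxone rule. Power stays at 79.4% to 80.1% at an assumed 0.02/day.
- **Sensitivity analysis:** first BM within 120 hours regardless of additional treatment. This needs no rescue times.
- **If any additional treatment was meant for both cohorts:** say so, define it for both (including whether standing as-needed laxatives count), and restate the power. It would be about 71%, 76% or 78% for a day 1, 2 or 3 start at an assumed 0.2/day.

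The cost is one SAP definition and one extra analysis. The ileus-only rule needs control treatment times that the plan already requires, plus the same times for naloxone patients. The any-treatment rule would need escalation times from 150 historical charts, whereas Study Design lists only the number of escalations.

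Two limits remain. Censoring at rescue can stay informative under any common rule, and differences in laxative practice between the cohorts can still bias the comparison. The sensitivity analysis compares naloxone plus usual care with usual care, so heavier laxative use in controls could dilute the effect.
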